6.2 IMPORTANT PROTOCOL DEVIATIONS

Data discrepancies and deviations from the CTP will be identified for all treated subjects.

Section 7.3 of the CTP: *Important protocol deviation (iPD) categories will be specified in the TSAP, iPDs will be identified no later than in the Report Planning Meeting, and the iPD categories will be updated as needed.*

Consistency check listings (for identification of deviations of time windows) and a list of protocol deviations (e.g. deviations in drug administration, in blood sampling times, etc.) will be provided to be discussed at the Report Planning Meeting (RPM). At this meeting, all manual deviations identified at the sites by the CRAs and deviations too complex to program will be reviewed by the trial team to decide which are considered important. For definition of important protocol deviations (iPD), and for the process of identification of these, refer to the Boehringer Ingelheim (BI) SOP "Identify and Manage Important Protocol Deviations (iPD)" ([2](#)).

If any iPDS are identified, they are to be summarised into categories and will be captured in the decision log. Categories which are considered to be iPDS in this trial are defined in [Table 6.2: 1](#). The decision on exclusion of subjects from analysis sets will be made at the latest at the Report Planning Meeting, after discussion of exceptional cases and implications for analyses. If the data show other iPDS, the definition below will be supplemented accordingly by the time of the Report Planning Meeting and will be documented in the decision log and in the iPDS specification file (3).

The iPDS will be listed in the CTR.

Table 6.2: 1 Important protocol deviations

Category/Code		Description
A		Eligibility Criteria
	A1	Critical inclusion/exclusion criteria violated
	A2	Withdrawal criteria as defined in the protocol met, but subject was not withdrawn
B		Informed Consent
	B1	Required informed consent not available/not done
C		Trial Medication and Randomization
	C1	Randomisation order not followed
	C2	Critical trial medication procedure violated
D		Concomitant medication
	D1	Improper medication washout
	D2	Prohibited medication use
	D3	Mandatory medication not taken/insufficient
E		Critical Study Procedure/Assessment
	E1	Improper primary endpoint assessment
	E2	Improper key secondary endpoint assessment
F		Safety Procedures/SAE Reporting
	F1	Critical safety procedure not followed
G		Privacy/Data Protection
	G1	Privacy and/or data protection violated
Q		Non-important COVID-19 Related
	Q1	Missed examination
	Q2	Missed visit
	Q3	Drug shipment

6.3 SUBJECT SETS ANALYSED

Section 7.3 of the CTP:

- *Treated set (TS): The treated set includes all subjects who were randomized and treated with at least one dose of investigational medicinal product. The treatment assignment will be determined based on the first treatment the subjects received. The treated set will be used for safety analyses.*
- *Pharmacokinetic parameter analysis set (PKS): This set includes all subjects in the treated set (TS) who provide at least one PK endpoint that was not excluded due to a protocol violation relevant to the evaluation of PK or due to PK non-evaluability (as specified in the following subsection 'Pharmacokinetics'). Thus, a subject will be included in the PKS, even if he contributes only one PK parameter value for one period to the statistical assessment. Descriptive [...] analyses of PK parameters will be based on the PKS.*

(...)

Pharmacokinetics

Plasma and urine concentration data and parameters of a subject will be included in the statistical PK analyses if they are not flagged for exclusion due to a protocol violation relevant to the evaluation of PK (to be decided no later than in the Report Planning Meeting) or due to PK non-evaluability (as revealed during data analysis, based on the criteria specified below). Exclusion of a subject's data will be documented in the CTR.

Relevant protocol violations may be

- *Incorrect trial medication taken, i.e. the subject received at least one dose of trial medication the subject was not assigned to*
- *Incorrect dose of trial medication taken*
- *Use of restricted medications*

Plasma and urine concentrations and/or parameters of a subject will be considered as non-evaluable, if for example

- *The subject experienced emesis that occurred at or before two times median t_{max} of the respective treatment (Median t_{max} is to be determined excluding the subjects experiencing emesis),*
- *Missing samples/concentration data at important phases of PK disposition curve.*

[figure not shown]
Plasma/urine concentration data and parameters of a subject which is flagged for exclusion will be reported with its individual values but will not be included in the statistical analyses.

Only concentration values within the validated concentration range and actual sampling times will be used for the calculation of pharmacokinetic parameters. Concentrations used in the pharmacokinetic calculations will be in the same format as in the bioanalytical report (that is to the same number of decimal places provided in the bioanalytical report).

The descriptive analysis of PK endpoints and concentrations will be based on the ADS ADPP and ADPC as described at the beginning of [Section 7](#).

Table 6.3: 1 Subject sets analysed

Class of endpoint	Subject set
TS	PKS
PK endpoints	X
Safety parameters	X
ECG endpoints	X
Demographic/baseline parameters	X
Important protocol deviations	X
Disposition	X

6.5 POOLING OF CENTRES

This section is not applicable, because the study was performed in only one centre.

6.6 HANDLING OF MISSING DATA AND OUTLIERS

Handling of missing data and outliers will be performed as described in the CTP, Section 7.5.

The only exceptions where imputation might be necessary for safety evaluation are AE dates. Missing or incomplete AE dates are imputed according to BI standards (see BI-KMED-BDS-HTG-0035) ([4](#)).

Missing data and outliers of PK data are handled according to BI standards (see BI-KMED-TMCP-MAN-0012 ([5](#)) and BI-KMED-TMCP-MAN-0014 ([6](#))).

6.7 BASELINE, TIME WINDOWS AND CALCULATED VISITS

The baseline value is defined as the last measurement before trial medication administration.

Section 6.1 of the CTP: *Exact times of measurements outside the permitted time windows will be documented. The acceptable time windows for screening and the end of trial examination are provided in the CTP Flow Chart.*

Trial measurements and assessments scheduled to occur 'before' trial medication administration at Day 1 are to be performed and completed within a 2 h-period prior to the investigational medicinal product administration (including blank values for PK). A blank urine sample for PK will be collected within 3 h before drug administration.

The acceptable deviation from the scheduled time for vital signs and ECG will be ± 10 min for the first 4 h after investigational medicinal product administration and ± 30 min thereafter. For laboratory test, the acceptable deviation is ± 30 min.

(...)

The acceptable deviation from the scheduled time for neurological tests is ± 45 min on Day 1 and ± 90 min for other days.

Adherence to time windows will be checked via the consistency check listings at the RPM.

Unscheduled measurements of laboratory data and vital signs data will be assumed to be repeat measurements of the most recent scheduled measurement (e.g. for follow-up or confirmation of a particular value). Therefore, unscheduled measurements will be assigned to the planned time point of the previous scheduled measurement.

There will be a centralised evaluation of the 12-lead ECG recordings at the time points and for the ECG recordings specified in Table 6.7: 1 below:

Table 6.7: 1 Time schedule of 12-lead ECG recordings

Visit	Day	Planned time [hh:mm] (relative to drug administration)	Study phase	Central evaluation
1	-28 to -1		Screening	NA
2	-1	-24:00	Pre-dose	Three triplicate ECGs**
	1	-01:00	Baseline	Triplet ECG*
		00:30	On treatment	Triplet ECG*
		01:00	On treatment	Triplet ECG*
		01:30	On treatment	Triplet ECG*
		02:00	On treatment	Triplet ECG*
		02:30	On treatment	Triplet ECG*

		03:00	On treatment	TriPLICATE ECG*
		04:00	On treatment	TriPLICATE ECG*
		06:00	On treatment	TriPLICATE ECG*
		08:00	On treatment	TriPLICATE ECG*
		12:00	On treatment	TriPLICATE ECG*
	2	24:00	On treatment	TriPLICATE ECG*
		34:00	On treatment	NA
	3	48:00	On treatment	NA
	4	72:00	On treatment	NA
3	15 to 17		End of trial examination	NA

* Central ECG lab evaluation will be performed for the first ECG of triplicate ECGs at every time point

** Will not be used for ECG analyses

Three triplicate ECGs will be recorded on Day -1 -24:00, but only the first triplicate will be transferred to the database. These values will not be used for the ECG analyses.

At all other time points, triplicate ECGs will be recorded, but only the first ECG of the triplicate will be transferred to the data base. The baseline value of an ECG variable is defined as the first single ECG of the triplicate at Day 1 prior to drug administration (-1:00).

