5.2.4 Electrocardiogram

5.2.4.1 12-lead resting ECG

Recording

Twelve-lead resting ECGs (I, II, III, aVR, aVL, aVF, V1 - V6) will be recorded using a computerised electrocardiograph at the time points given in the [Flow Chart](#). Precise electrode placement will be performed according to the method of [REDACTED] and [REDACTED], modified by [REDACTED] and [REDACTED], i.e. hips and shoulders instead of ankles and wrists. Precise electrode placement will be marked with an indelible mark on the skin to allow reproducible placement throughout the trial.

To achieve a stable heart rate at rest and to assure high quality recordings, the site personnel will be instructed to assure a relaxed and quiet environment so that all subjects are at complete rest.

All ECGs will be recorded for 10 s after subjects have rested for at least 5 min in a supine position. ECG recording will always precede all other trial procedures scheduled for the same time, except for blood drawing from an intravenous cannula that is already in place, to avoid compromising ECG quality.

ECGs will be recorded as single ECGs or as triplicate ECGs, i.e. three single ECGs recorded within 180 s, as indicated in the Flow Chart.

ECGs may be repeated for quality reasons due to, for instance, alternating current artefacts, muscle movements, or electrode dislocation. For repetition within triplicate ECGs, the time window of 180 s applies as well. The repeat ECGs are assigned to the respective scheduled time point.

Additional (unscheduled) ECGs may be collected by the investigator for safety reasons. These ECGs are assigned to the prior scheduled time point in the Sponsor's database.

Storage

All ECGs will be stored electronically in the System provided by [REDACTED].

Data transfer

All triplicate ECGs will be transferred electronically to the central ECG laboratory [REDACTED] for evaluation.

Proprietary confidential information © 2020 Boehringer Ingelheim International GmbH or one or more of its affiliated companies

In case of ECGs repeated due to quality reasons, only the repeated ECG recordings will be transferred to the central ECG lab, whereas the initially recorded ECGs will be discarded. Unscheduled ECGs, i.e. those taken for safety reasons, will be transferred to the central ECG lab, but will not be included into the statistical analysis of interval lengths.

Data transfer from the central ECG lab to the sponsor is described in a document that is filed in the TMF.

Evaluation

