a) Central ECG lab

Central ECG lab evaluation will be performed (during the trial and/or after the trial) for first ECG of triplicate ECGs at every time point. For baseline, all three ECGs of the triplicate ECG at Day 1 pre-dose will be evaluated. This will include the determination of cardiac QRS-axis, as assessed by the ECG machine's algorithm, as well as the intervals RR, PR, QRS, and QT measured semi-automatically. Heart rate (HR) and the QT interval corrected for HR, i.e. QTcF and QTcB, will be determined by the sponsor (see trial statistical analysis plan [TSAP] for details).

All semi-automatic interval measurements in one subject will be performed on the same lead. The intervals will be measured from four cardiac cycles (beats) in lead II. If lead II shows a flat T wave, or is not measurable for any reason, lead V5 will be used. If lead V5 is not measurable, then lead I will be used. The lead actually used will be reported in the CTR. For automatic interval measurements no lead will be provided

For blinding arrangements see Section [4.1.5.1](#). No more than two blinded readers will evaluate all ECGs of the trial. ECGs from a particular subject should be evaluated by a single reader. For quality assurance and control of the measurements, all ECGs of a subject will be subsequently reviewed by the ECG technician's supervisor, or his/her designee, to assess the overall variance of the measured intervals, to detect accidental switching of leads and/or false subject assignments of the ECGs. After quality control, the fiducial point markings will be reviewed by the cardiologist assigned to the trial.

Evaluation of ECGs will comply with the ICH E14 guidance document and supplements [[R07-4722](#), [R16-0366](#)] as well as the FDA requirements for annotated digital ECGs [[R09-4830](#)].

b) Trial site

All local ECGs will be evaluated by the investigator or a designee.

For the inclusion, or exclusion, (see Section [3.3](#)) of a subject and for the assessment of cardiac safety during the trial, the QT and QTcB values generated by the computerised ECG system, or their manual corrections by the investigators, will be used. In doubtful cases, ECGs may be sent upfront, i.e. prior to the regular data transfer, for cardiologic assessment by the central lab. In this case, these centrally measured results would overrule any other results obtained.

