Adverse events will be coded using the Medical Dictionary for Regulatory Activities (MedDRA). Frequency, severity, and causal relationship of AEs will be tabulated by treatment, system organ class and preferred term. SAEs, AESIs (see Section [5.2.6.1](#)) and other significant AEs (according to ICH E3) will be listed separately.

Previous and concomitant therapies will be presented per treatment group without consideration of time intervals and treatment periods.

Laboratory data will be compared to their reference ranges. Values outside the reference range as well as possibly clinically significant values will be highlighted in the listings. Additionally, differences from baseline will be evaluated.

Vital signs or other safety-relevant data will be assessed with regard to possible on-treatment changes from baseline.

The ECG variables QT, HR, QTcF, QTcB, PR, QRS, and RR obtained from the centralised evaluation of 12-lead ECG recordings will be the basis for the derivation of quantitative and categorical ECG endpoints. These endpoints and their analyses will be described in the TSAP.

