4. CHANGES IN THE PLANNED ANALYSIS OF THE STUDY

The study was prematurely stopped after the first dose group (25mg BI 894416) due to a disadvantageous benefit risk ratio based on newly received data from another study with BI 894416.

Consequently, only a subset of the analyses planned in the CTP will be performed. Tables will be provided for disposition, demography, adverse events and standard safety analysis (including the primary endpoint) and for PK endpoints (including the secondary endpoints). For all study endpoints, listings will be provided. That means, for several variables, only listings will be provided and no descriptive analysis will be carried out. This applies to, for example, medical history, concomitant medication and non-drug procedures, laboratory data, vital signs and ECG.

As there is only one dose group available, no dose proportionality analysis will be done. Secondary endpoints (AUC_{0-∞} and C_{max} of BI 894416) will be analysed descriptively only.

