7.8.4 ECG

Continuous safety ECG monitoring:

ECG recordings will be checked by the investigator for pathological results. Clinically relevant abnormal findings for ECG will be listed under 'Relevant Medical History / Baseline Conditions' (if they pre-exist prior to trial inclusion) or will be reported as AEs (if they occurred on treatment), and will be analysed as such. No separate ECG monitoring listing will be provided.

12-lead ECG:

Abnormal findings will be reported as baseline conditions (at screening) or as AEs (during the trial) if judged clinically relevant by the investigator, and will be analysed as such.

Additionally, a dataset of quantitative and categorical ECG endpoints will be provided to [REDACTED] for analysis by an ECG programmer at BI.

Listings of individual data of ECG endpoints will be shown in Appendix 16.2. Occurrences of notable findings will be flagged. Comments regarding the ECGs will be listed.

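### The protocol has all three Day 1 pre-dose ECGs centrally evaluated for baseline; the SAP evaluates, transfers and uses only the first, without declaring the change, which adds random error to ECG changes from baseline

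*SAP*

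**What the plan says.** Protocol 5.2.4.1, under central ECG lab evaluation, has the first ECG of each triplicate read at each time point, with one exception: "For baseline, all three ECGs of the triplicate ECG at Day 1 pre-dose will be evaluated". Protocol 7.3.4 then says that the ECG variables "obtained from the centralised evaluation of 12-lead ECG recordings will be the basis for the derivation of quantitative and categorical ECG endpoints", and leaves the endpoints and their analyses to the SAP.

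SAP 6.7 keeps the general rule and drops the exception in three places:

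- **Central evaluation.** The footnote to Table 6.7: 1, which is attached to the -1:00 baseline row as well as the post-dose rows, reads "Central ECG lab evaluation will be performed for the first ECG of triplicate ECGs at every time point".
- **Transfer.** At every time point other than Day -1, "only the first ECG of the triplicate will be transferred to the data base".
- **Definition.** "The baseline value of an ECG variable is defined as the first single ECG of the triplicate at Day 1 prior to drug administration".

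SAP Section 4 sets out the changes that follow from stopping after the 25 mg group. ECG appears there only among the variables that will be listed and not summarised: "This applies to, for example, medical history, concomitant medication and non-drug procedures, laboratory data, vital signs and ECG". The number of baseline ECGs is not mentioned, and the history table in SAP Section 10 records no change. SAP 7.8.4 keeps individual ECG listings and adds that "a dataset of quantitative and categorical ECG endpoints will be provided to" a recipient whose name is redacted, for analysis.

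**The concern.** The two documents cannot both be followed: the central laboratory reads either three tracings at baseline or one. The protocol gives baseline as the reason for the extra readings, and under the SAP they serve no purpose. A reader of SAP Section 4 would assume that the protocol's provision still stands.

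Statistically, baseline is the value whose error matters most in a change analysis, because it is subtracted from every later reading of the same subject. A single tracing carries its full replicate error into all 11 of that subject's post-dose changes. Averaging three tracings cuts that part of the error variance to one third. The first-in-man trial gives a reason to care: Protocol 1.4.2 reports a dose- and concentration-dependent QTcF increase there, with a predicted mean of 5.9 ms at the 70 mg exposure (upper 90% limit 10.5 ms). Avoidable noise of a few milliseconds is not negligible beside effects of that size.

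**Working it through.** The plan states no figure for ECG precision, so there is none to reproduce.

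**Inputs from the documents**

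- Baseline ECGs centrally evaluated: 3 (Protocol 5.2.4.1) against 1 (SAP 6.7).
- Post-dose ECGs centrally evaluated per time point: 1 in both documents.
- Post-dose time points with central evaluation in SAP Table 6.7: 1: 0:30, 1:00, 1:30, 2:00, 2:30, 3:00, 4:00, 6:00, 8:00, 12:00 and 24:00, which is 11.
- Subjects analysed: 6 on 25 mg and 2 on placebo (SAP 6.1).

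**Assumed inputs**

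- e is the replicate variance within a triplicate, and b is the within-subject variance between time points. Errors are independent. The documents give neither value, so the ratio b/e is varied from 0 to 3.

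**Number of changes**

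Per ECG variable: 6 × 11 = 66 on 25 mg and 2 × 11 = 22 on placebo, 88 in total. This is a maximum, with a change at every central time point and no missing tracing.

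**Variance of one change from baseline**

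- Single baseline ECG: Var = (b + e) + (b + e) = 2(b + e).
- Mean of three baseline ECGs: Var = (b + e) + (b + e/3) = 2b + 4e/3.
- Difference: 2e/3, which is positive whenever there is any replicate error.
- Relative reduction with the mean of three: (2e/3) / [2(b + e)] = (1/3) / (1 + b/e).
- SD inflation under the SAP rule: √[2(b + e) / (2b + 4e/3)] − 1.

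| b/e | Variance reduction with mean of three | SD inflation under SAP rule |
|---|---|---|
| 0 | 33.3% | √(2/1.333) − 1 = 22.5% |
| 1 | 16.7% | √(4/3.333) − 1 = 9.5% |
| 2 | 11.1% | √(6/5.333) − 1 = 6.1% |
| 3 | 8.3% | √(8/7.333) − 1 = 4.4% |

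Beyond this range the inflation keeps shrinking. With a replicate SD of 3 ms and a between-time SD of 8 ms (b/e = 64/9, about 7) it is about 2% (SD 12.08 against 11.83 ms).

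**Illustration in milliseconds**

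Assume a total within-subject SD of a single reading of 5 to 10 ms, so that b + e is 25 to 100 ms².

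- SAP rule: √50 to √200 = 7.1 to 14.1 ms.
- Mean of three, b/e = 0: √33.3 to √133.3 = 5.8 to 11.5 ms.
- Mean of three, b/e = 3: √45.8 to √183.3 = 6.8 to 13.5 ms.

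**Shared error**

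The same baseline error enters all of a subject's changes. With b = 0, the correlation between two post-dose changes is e/(2e) = 0.50 with a single ECG and (e/3)/(4e/3) = 0.25 with the mean of three. More time points therefore do not average a poor baseline away.

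**The case against.** The conflict over central evaluation is not in dispute. The case on the other side concerns its weight.

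- **The protocol requires evaluation, not averaging, and leaves ECG endpoints to the SAP.** This stands in part. The SAP may define the baseline value, and the added error is measured against a mean of three that no document prescribes. But the number of baseline tracings to be read is fixed in the protocol and is not left to the SAP.
- **The SAP does not commit to ECG changes from baseline.** SAP 7.8.3 promises change-from-baseline listings for vital signs; SAP 7.8.4 does not say this for ECG. So 88 is a ceiling. Still, the SAP defines an ECG baseline and passes on a dataset of ECG endpoints, so any change taken from those data inherits the single-tracing error.
- **The size rests on assumptions.** This stands. The 22.5% figure is a limiting case with no variation between time points over 24 hours, and 4.4% is not a floor.
- **The consequence is small.** This also stands. The trial ended after one dose group of eight subjects, ECG is neither a primary nor a secondary endpoint, and eligibility and on-trial cardiac safety normally rest on the site's own QT and QTcB values (Protocol 5.2.4.1).
- **The SAP is based chiefly on Protocol Section 7, which sets no ECG baseline.** True, but a departure from an assessment section that alters the baseline data still belongs in the list of changes.

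**Conclusion.** The concern holds. The SAP departs from Protocol 5.2.4.1 on how many Day 1 pre-dose ECGs are centrally evaluated, and the departure is not declared. Against a mean-of-three baseline, the single-ECG rule inflates the SD of an individual change by 4.4% to 22.5% for b/e between 3 and 0, and by less if variation between time points dominates further. That range depends wholly on the assumed variance ratio and on independent errors.

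This is random error, not bias. It reaches the listed ECG data and the ECG endpoint dataset wherever a change from baseline is taken. It does not reach the primary endpoint, the PK endpoints or on-trial cardiac safety decisions. The visible text does not say how notable findings are flagged relative to baseline, so no effect on flags is claimed. The point should be corrected because it is a plain inconsistency with an inexpensive remedy, but it does not threaten the trial's main conclusions.

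**What to change.** In SAP 6.7:

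1. Define the baseline of each ECG variable as the arithmetic mean of the three centrally evaluated ECGs of the Day 1 pre-dose (-1:00) triplicate.
2. Have all three transferred to the database.
3. Change the footnote marking in Table 6.7: 1 so that the baseline row shows all three ECGs evaluated.

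The opening sentence of SAP 6.7 gives a general baseline rule based on the last pre-dose measurement. The ECG-specific definition already takes precedence; a short clause exempting ECG would make that explicit.

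If the second and third tracings were not read and will not be, keep the single-ECG baseline and declare it in SAP Section 4 as a departure from Protocol 5.2.4.1.

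The cost is SAP wording and two more records per subject, 2 × 8 = 16 in all. If the readings planned in the protocol were not made, 16 further central readings are needed; Protocol 5.2.4.1 allows central evaluation after the trial. The transfer specification may need a matching edit, since the protocol says: "Data transfer from the central ECG lab to the sponsor is described in a document that is filed in the TMF".
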